RATIONALE	Our study will test the feasibility of providing whole blood (WB) for resuscitation of adult male trauma patients in hemorrhagic shock and determine the effects of WB on clinical outcomes as well as the effects on coagulation, fibrinolysis, and inflammation, and hemolytic transfusion reactions compared to standard blood component therapy.
STUDY DESIGN	Prospective cohort study
PRIMARY OBJECTIVE	1. Compare volume of blood transfusion within 24 hours of admission between patients receiving whole blood and standard component therapy.
SECONDARY OBJECTIVES	The study will also compare: 1. Functional coagulopathy as measured by thromboelastography;

	
 2. 30-day mortality; 3. Number of units of blood products transfused by component/product; 4. Complications; 5. Hemolysis; 6. Wastage of blood units.
NUMBER OF PATIENTS	
Whole blood arm - 49 male patients over apparent age 18. Component therapy arm –49 male and female patients over apparent age 18.

PATIENT SELECTION CRITERIA	
Inclusion Criteria:
 
 • Whole blood arm: Male trauma patients over apparent age 18 with massive transfusion activation and presenting systolic blood pressure <100, who are receiving or will receive whole blood for initial resuscitation • Component therapy arm: Male and female trauma patients over apparent age 18 with massive transfusion activation and presenting systolic blood pressure <100, who have received, are receiving or will receive component therapy for initial resuscitation. 
Exclusion Criteria:
 
 • Patients with burns over >20% total body surface area
TEST PRODUCT, DOSE, AND ROUTE OF ADMINISTRATION	
Group O+ whole blood stored at 1-6 °C for up to 10 days. Patients may receive up to 4 units during the initial phase of the proposed study, to be increased to up to 6 units (see 5.2 Safety Evaluations) Product is administered to replace ongoing blood loss and restore/maintain hemodynamic stability and hemostasis. Product will be transfused intravenously as needed during initial traumatic resuscitation only. Following administration of whole blood if further transfusion is needed during initial trauma resuscitation, or after resuscitation is completed, the patient will receive standard

PI: [name]

	component therapy (packed red blood cells, plasma and platelets in a 1:1:1 ratio).

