4 STUDY DESIGN

4.1 Study Overview

This is a single center, prospective cohort study. Enrollment of approximately 98 patients is planned, 49 receiving whole blood and 49 receiving component therapy. This is an observational study planned during initiation of a change in practice at our institution initially allowing up to 4 units of whole blood transfusion for adult male trauma patients. If initial patients receiving whole blood show no evidence of hemolysis and thrombocytopenia compared to patients receiving component therapy, up to 6 units of whole blood transfusion will be allowed (see below, and section 5.2, Safety Evaluations). Patients in the whole blood, or index, group are adult male trauma patients presenting in hemorrhagic shock (systolic blood pressure < 100) requiring massive transfusion activation who receive whole blood for resuscitation. Two control groups will be utilized. The prospective control group consists of adult male patients who present during times when whole blood is not available, as well as adult female patients, presenting in hemorrhagic shock (systolic blood pressure <100) requiring massive transfusion activation. Additionally, a second control group consisting of historical

PI: [name]

controls receiving component therapy will be analyzed (see Section 6, Patient Selection, for details of index and control groups).

All patients will have, in addition to standard labs, additional labs drawn for thromboelastography, platelet function determination, and coagulation factor levels (see Section 9.1.6, Other Clinical Procedures, for details of specific lab tests and timing).

Patients who meet all inclusion criteria and none of the exclusion criteria will be enrolled into the study.

Total duration of patient participation will be approximately 1 year (365 days), or the duration of the hospital stay, whichever is shorter. This includes up to 5 days of laboratory testing during initial resuscitation and subsequent admission, and up to one year of follow up via chart review if the patient remains in the hospital. Total duration of the study including recruitment and follow up is expected to be 2 years.

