6 PATIENT SELECTION

6.1 Study Population

All trauma patients who present with SBP<100 who require activation of the massive transfusion protocol and who do not have severe burns (>20% total body surface area) will be eligible for enrollment.

Enrollment of male and female patients:

PI: [name]

At UCLA and at least two other institutions²⁸ the standard of care for traumatic resuscitation for adult males is either:

- 1) Low anti-A anti-B titer (<1:100) group O+ whole blood
or, when whole blood is not available,
- 2) Component therapy, consisting of group O+ PRBCs, group AB or A plasma, and untyped platelets

The standard of care for adult females is component therapy, consisting of group O- PRBCs, group AB or A plasma, and untyped platelets. Group O- whole blood is not available at our institution at this time. During a critical traumatic resuscitation, it is often impossible to determine precise age and menopausal status before initiation of transfusion. In order to avoid any possibility of alloimmunization of reproductive-age females, the UCLA Blood and Blood Derivatives Committee has approved group O+ whole blood only for use in males.

The index and control groups in the study therefore consist of:

- 1) Index group: male trauma patients presenting with SBP<100 who require activation of the massive transfusion protocol and who do not have severe burns >20% TBSA who receive whole blood;
- 2) Prospective control group: Prospectively-identified cohort of patients who present during the study with SBP<100 who require activation of the massive transfusion protocol and who do not have severe burns >20% TBSA but who are either not eligible or not able to receive whole blood. This category consists of patients who are female (who are not eligible to receive whole blood) and male patients who present when whole blood is out of stock;
- 3) Historical control group: male trauma patients who presented with SBP<100 who required activation of the massive transfusion protocol and who did not have severe burns >20% TBSA who received component therapy for traumatic hemorrhage requiring massive transfusion protocol activation, during the 5 years prior to initiation of the study.

A mixed effects linear regression model will be used to adjust for confounding variables, including sex.

Enrollment of patients of unknown precise age:

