6.2 Inclusion Criteria

All trauma patients who present with SBP<100 who require activation of the massive transfusion protocol and who do not have severe burns (>20% total body surface area) will be eligible for enrollment. The study plans to include all such patients who present during the study period of approximately 2 years.

Within this group of patients, all adult male patients who received or will receive whole blood are eligible for inclusion in the whole blood group. All adult male patients who received or will receive component therapy initially are eligible for inclusion in the component therapy group. All adult female patients are eligible for inclusion in the component therapy group.

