8 STUDY TREATMENTS

8.1 Method of Assigning Patients to Treatment Groups

Treatment groups are not assigned as this is an observational study. Treatment is determined by the eligibility of the patient (male or female) and the availability of whole blood when the patient presents. Adult male patients meeting eligibility who have

PI: [name]

received or will receive whole blood for traumatic resuscitation will be enrolled in the whole blood group. Enrollment of 49 patients receiving whole blood is planned. Adult male patients meeting eligibility criteria who present when whole blood is not available will receive component therapy and will be enrolled in the component therapy group. Enrollment of 49 control (component therapy group) patients is planned. Female patients meeting eligibility criteria will also be included in the component therapy group (see Section 6.1, Study Population, for rationale).

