17.3 Waiver of Informed Consent

Informed consent and HIPAA authorization have been waived by the Institutional Review Board because 1) both whole blood and component therapy are considered standard of care for adult male trauma patients, and availability of whole blood (as well as patient gender) determines which therapy a patient will receive; and 2) due to the emergent nature of traumatic resuscitation, it is not possible to inform patients of the

PI: [name]

study prior to initiating study-related testing (additional blood draw for TEG) or prior to initiation of therapy by the clinical team.

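### Control men are defined by product first received in 6.2 and the synopsis, but by whole blood being unavailable at arrival in 4.1, 6.1 and 8.1

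*Protocol*

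**What the plan says.** Two kinds of definition appear in the protocol.

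**By stock.** Section 4.1 says: "The prospective control group consists of adult male patients who present during times when whole blood is not available", with adult women added. Section 6.1 describes the prospective controls as patients who are ineligible for whole blood or cannot receive it, and lists only two kinds: women, and "male patients who present when whole blood is out of stock". Section 8.1 says: "Adult male patients meeting eligibility criteria who present when whole blood is not available will receive component therapy", and enrolls them in the component group.

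**By product received.** Section 6.2 says: "All adult male patients who received or will receive component therapy initially are eligible for inclusion in the component therapy group". It sets no condition on stock. The synopsis describes component-arm patients as those "who have received, are receiving or will receive component therapy for initial resuscitation", again without a stock condition. The analysis sets in 15.1 are also worded by product received.

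On how treatment comes about, 8.1 says: "Treatment is determined by the eligibility of the patient (male or female) and the availability of whole blood when the patient presents". Section 17.3 gives the same account in support of the consent waiver: "availability of whole blood (as well as patient gender) determines which therapy a patient will receive".

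Section 13 lists a switch from components to whole blood as a protocol violation. Section 15.3 tests the primary endpoint with a t-test or a Wilcoxon rank sum test, with no covariates.

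**The concern.** The study is observational, so its credibility depends on why a patient got one product and not the other. For men, the protocol gives one reason: whether whole blood was there when they arrived. Stock has a fair claim to be unrelated to how badly a given man is bleeding. A rule based on the product received first has no such claim, because any reason for giving components then qualifies a man as a control.

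These men would enter the unadjusted primary comparison (if they have no severe TBI) and the prospective secondary comparisons. Eligibility is settled in the protocol itself, and 6.2 plans to include every qualifying patient who presents. Study staff would therefore have to classify such a man, and the protocol gives them two answers.

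**Working it through.** **Step 1. The plan's own figure.** 49 per group less about 18 with severe TBI leaves 49 − 18 = 31. At 35–40%, the number excluded is 0.35 × 49 = 17.2 to 0.40 × 49 = 19.6, leaving 29.4 to 31.9. The figure of about 31 reproduces, and this point does not change it. One control man classified differently is 1/31 = 3.2% of the planned evaluable control group.

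**Step 2. Apply both rules to each kind of eligible man.**

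| Man | By stock (4.1, 6.1, 8.1) | By product (6.2, synopsis) |
|---|---|---|
| None available at arrival, components only | Control | Control |
| In stock, whole blood first | Whole blood | Whole blood |
| In stock, components only | No group | Control |
| In stock, components first, then whole blood | Whole blood (he received it) | Both groups |

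The rules agree on the first two rows and part on the last two. The fourth row falls in both groups under 6.2 because that section admits to the whole blood group every man who received whole blood, and to the component group every man who received components initially. Sections 4.1 and 6.1 are exclusive in form. Section 8.1 does not say only, but its account of how treatment is determined leaves no other route for a man.

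**Step 3. What the third row does to the comparison.** The protocol gives no inputs, so this is symbolic. Consider men only, and assume stock is unrelated to need. Among men arriving with stock, let a share p get components only, with mean need s higher (or lower, if s is negative) than μ, the mean need of those given whole blood. Men arriving without stock then have mean need μ + ps. Let f be the share of control men who belong to the third row. The difference in need, control men minus whole blood men, is:

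- Controls as in 6.2: (1 − f)ps + fs = s[p + f(1 − p)].
- Controls limited to stock-out men, in-stock component men dropped: ps.
- All men grouped by stock at arrival, whatever they received: (μ + ps) − (μ + ps) = 0.

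All three are zero if p = 0. The second is not zero when p > 0, because the whole blood arm still lacks the in-stock men who got components. Tightening the definition alone therefore reduces the imbalance without removing it. In the pooled primary comparison, the male difference is weighted by the share of controls who are men, which the protocol does not state.

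**Step 4. Could the planned data show it?** The chart-review list in 10.1 does not name stock at arrival or the reason for components. The adjusted model in 15.4 names sex, age, comorbidities, injury severity, shock physiology and rapid transfuser use, but neither of those two items.

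**The case against.** The strongest reply is that the two rules coincide if care follows the protocol. Sections 8.1 and 17.3 say that sex and availability determine treatment, and 6.1 gives components as the standard for men only when whole blood is not available. On that account, men who receive components first are the men who arrived without stock, and the third row of the table is empty. The word initially in 6.2 may also have been meant only to classify patients by first product, since whole blood patients later move to components. This stands as far as it goes: the rules part only where practice departs from the stated mechanism. It does not remove the conflict, because 6.2 gives such a man an answer and 4.1 and 6.1 give a different one. Section 13 shows that patients who start on components and then receive whole blood were foreseen.

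Three stronger readings are tempting and are not supported.

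- A reader might infer that clinicians choose components for some men and that confounding by indication is present. No section describes such a choice. The switching violation does not show one either, since stock could arrive during resuscitation.
- A reader might put a number on the bias. Neither the share of such men nor their difference in need is in the protocol. The design's detectable difference belongs to the pooled 31 versus 31 comparison with women among the controls, and 15.1 lists no prospective male-only set to compare against.
- A reader might infer that stock status would be lost for good. Section 8.5 requires ongoing blood bank records of units dispensed and returned for each patient, and 8.4 describes a target inventory of 12 units split between the trauma bay and the blood bank. Reconstruction may be possible.

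The planned regression adjustment, which the synopsis places under its primary analysis plan, would help in part. The test named for the primary endpoint in 15.3 remains unadjusted.

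**Conclusion.** The inconsistency is certain, because it is in the text. Section 6.2 and the synopsis omit the availability condition found in 4.1, 6.1 and 8.1, so an in-stock man given components is a control under one rule and unplaced under the other, and a man who switches can fall in both groups under 6.2. The consequence is conditional: the wording leaves room for confounding by indication in an unadjusted primary comparison, of unknown size and direction, and of no size if such men do not occur. Step 3 also assumes that stock is unrelated to need. The matter is cheap to settle and should be settled in the protocol.

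**What to change.** 1. Reconcile 6.2 and the synopsis with 4.1, 6.1 and 8.1 so that there is one definition of control men, and check that 15.1 follows it. State what counts as available (trauma bay, blood bank or either) and which group a man who switches belongs to. This concerns who is counted as a control, not which product anyone receives.
2. Record whole blood stock in the trauma bay and the blood bank at each eligible male arrival, taken from blood bank records.
3. Keep men given components despite stock in the study and report them separately.
4. Add a sensitivity analysis that groups all eligible men by stock at arrival, whatever product they received. Step 3 shows why it is needed: removing the in-stock component men from the controls leaves the whole blood arm selected.

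The cost is a wording change, one data field and one analysis. The control set may be slightly smaller. The stock-grouped analysis will dilute any product effect to the extent that in-stock men did not receive whole blood.

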6.3 Exclusion Criteria

1. Patients with burns over >20% total body surface area
2. Patients who appear to be under age 18

7 CONCURRENT MEDICATIONS

All patients should be maintained on the same medications throughout the entire study period, as medically feasible, with no introduction of new chronic therapies related to the study.

7.1 Allowed Medications and Treatments

There are no prohibited medications or treatments.

8 STUDY TREATMENTS

8.1 Method of Assigning Patients to Treatment Groups

Treatment groups are not assigned as this is an observational study. Treatment is determined by the eligibility of the patient (male or female) and the availability of whole blood when the patient presents. Adult male patients meeting eligibility who have

PI: [name]

received or will receive whole blood for traumatic resuscitation will be enrolled in the whole blood group. Enrollment of 49 patients receiving whole blood is planned. Adult male patients meeting eligibility criteria who present when whole blood is not available will receive component therapy and will be enrolled in the component therapy group. Enrollment of 49 control (component therapy group) patients is planned. Female patients meeting eligibility criteria will also be included in the component therapy group (see Section 6.1, Study Population, for rationale).

8.2 Blinding

The study is not blinded.

8.3 Formulation of Test and Control Products

1. Test Product: Low-antibody (anti-A/anti-B) titer ($<1:100$) Group O+ banked whole blood stored at 1-6 °C for up to 10 days. After collection, product undergoes infectious disease and immunohematology testing per regulatory requirements and leukocyte-reduction with a platelet-sparing filter.
2. Control Product: Component therapy manufactured according to standard practices, consisting of packed red blood cells, thawed fresh frozen plasma and platelets in a 1:1:1 ratio.

8.3.1 Packaging and Labeling

Whole blood is supplied by the UCLA Blood Bank in bags containing approximately 250 milliliters of product. It is labeled with a large-print, brightly-colored label identifying it as whole blood.

8.4 Supply of Study Drug at the Site

The UCLA Blood & Platelet Center will identify repeat volunteer male whole blood donors to maintain a predetermined inventory of 12 units of low-titer ($<1:100$) O-positive whole blood. These donors will be identified by titrating the retention samples from a prior donation. The study will be explained to potential donors as a recruitment tool.

All donors of whole blood units will be tested for transfusion-transmitted infectious diseases, identical to the AABB and FDA regulations for all blood donors. Donor infectious disease testing is performed at CTS (Creative Testing Solutions) in Tempe, Arizona; the average turn-around time for completion of testing and blood availability in inventory is 48 hours. Whole blood units will undergo pre-storage leukoreduction with a platelet-sparing filter (Imuflex WB-SA, Terumo, Tokyo, Japan) and then stored at 1-6°C

PI: [name]

for 10 days. If not used by day 10, units will be fractionated into PRBC units to be released into general inventory for transfusion, and plasma which will be discarded. The goal is to maintain up to 12 units of low-titer type O-positive whole blood weekly. 6 units will be stored in the Trauma Bay blood refrigerator, and 6 units will be stored in the blood bank.

8.4.1 Dosage/Dosage Regimen

Adult male patients may receive up to 4 units of whole blood if needed during initial traumatic resuscitation in the initial phase of the study, and up to 6 units if deemed to be safe (see section 5.2, Safety Evaluations).

8.4.2 Dispensing

The blood bank dispenses all blood products.

8.4.3 Administration Instructions

Blood products are transfused intravenously.

8.4.4 Storage

Whole blood will be stored by the study site in a refrigerator designated for the storage of blood products maintained at 1-6°C. If the temperature of study drug storage in the clinic/pharmacy exceeds or falls below or above this range, this will be reported to the Sponsor/Investigator or designee and captured as a deviation.

8.5 Study Drug Accountability

An accurate and current accounting of the dispensing and return of study drug for each patient will be maintained on an ongoing basis by a member of the study site staff at the blood bank. The amount of study drug dispensed and returned will be recorded in blood bank accountability records. The study monitor will verify these documents throughout the course of the study.

9 STUDY PROCEDURES AND GUIDELINES

A Schedule of Events representing the required testing procedures to be performed for the duration of the study is diagrammed in Appendix 1.

Due to the emergent nature of treatment, and the fact that both whole blood and component therapy are considered standard of care for traumatic resuscitation of adult males, the UCLA Institutional Review Board has waived the requirement for informed

PI: [name]

consent and Health Insurance Portability and Accountability Act (HIPAA) authorization. As an FDA approved product, whole blood is not considered an investigational treatment by the Institutional Review Board and therefore these requirements have been waived for the entire study. Patients will be informed of which product they received and of the study by their clinical providers, but not directly by study personnel.

9.1 Clinical Assessments

9.1.1 Concomitant Medications

All concomitant medication and concurrent therapies will be documented on admission or as soon as possible thereafter. Dose, route, unit frequency of administration, and indication for administration and dates of medication will be captured.

9.1.2 Demographics

Demographic information (date of birth, gender, race) will be recorded on admission.

9.1.3 Medical History

Relevant medical history, including history of current disease, other pertinent respiratory history, and information regarding underlying diseases will be recorded on admission.

